At the end of each intervention session and at the end of each intervention block, a joint discussion will be held to craft a plan for parents to implement. This will include the functional goals to be embedded, specific strategies to be used that the parent has been coached in and the home routines that the parent plans to implement. Intervention related resources such as description of strategies and examples of embedding within routines and documents on the plan will be shared with parents for their reference.

Program Timeline

While set timeframes for assessments, intervention and reviews are important, this study will be implemented under routine operational conditions of the clinical service. The standard practice of having the same therapist for each session for continuity will be adopted. Scheduling challenges are an unavoidable field condition. This is compounded by the need for rescheduling of sessions at times, such as when a child/family member or therapist is unwell. For these reasons, the duration of time to complete each intervention block may vary slightly for each child. It may also vary between the intervention and control groups.

In general, where delays from scheduling occur, each child will move to the next phase of the study (i.e. intervention and follow-up reviews) only when they have completed all planned sessions in the previous phase (e.g., intervention will only begin after all baseline assessments have been completed). These are recognised as limitations of the study design and will be considered when interpreting the study findings.

Follow-up and Review (Standard Program and Telerehab Program)

Midterm Progress Review: Visit 7 to Visit 11

Paediatrician Review (two visits): The paediatrician will review the child's general developmental profile, progress and child and family needs. The clinician will make appropriate recommendations and referrals as needed.

Therapist Review (two visits): Therapists will review the child's developmental profile on the FSC and JERI to track progress on the intervention plan and for program evaluation purposes. A cost survey will also be conducted with parents during these reviews by a member of the study team to identify any changes to household income and cost burden. If parents are unable to complete the survey during their session, they will be sent the survey through email or asked to answer the questions over a phone call.

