Children also continue to remain as CDU patients under the care of their doctors until age 7, regardless of whether they have been enrolled to an EIPIC or private service. As such, study participants who have been transferred to an EIPIC will still be assessed per protocol for Midterm Progress Reviews and Final Reviews and Assessments. As far as possible, these assessments will be scheduled to coincide with their doctor's follow-up at the CDU as part of standard care.

Logic Model for Telerehab Program

Evaluation Framework

Literature Review

There is a dearth of published research on the use of telehealth in coaching for parents of children with autism spectrum disorders. A literature search found only two representative studies (Vismara et al, 2013 and Maedan et al, 2016) both from the United States and with small sample size.

One study followed eight families over a 12-week online video conference based intervention with three month follow up. Parents reported a better understanding of and appreciation for helping their children new skills, as well as increased confidence in addressing their child's needs and sharing information with other caretakers. The other described a similar Internet-Based Parent-Implemented Communication Strategies (i-PiCS) parental coaching program with 3 mother-child dyads and found positive changes in children's communication skills with the implementation of the strategies taught in coaching. As illustrated by the sample size <10 in each, neither previous study followed a rigorous RCT methodology but both studies highlighted the potential of telehealth as a feasible service-delivery option for parental coaching and called for further more robust studies of telehealth interventions with a greater diversity of participants.

Evaluation Questions

Effectiveness Trial

Primary Research Question: Is the tele-health intervention as effective as standard care in improving short and long-term outcomes for children and parents?

Process Evaluation

- How feasible and acceptable is the tele-health intervention?
- What features or conditions make the tele-health intervention more or less effective?
- What could be improved with acceptability, feasibility and scalability in mind?

Cost-Effectiveness

Is the tele-health intervention cost-effective (cost-saving) relative to standard care?

Indicators and Outcomes

Evaluation Question	Primary indicator required	Measurement & Reference	Expected change

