Patients will be recruited for the program after obtaining a preliminary diagnosis of ASD from the developmental paediatrician. ADOS-2 will be administered to confirm the diagnosis and thus participation in the research study. We will not be advertising this study to the public.

Pilot

An initial pilot feasibility study with 6 children and families will be conducted at the start of the project to identify any practical issues or weaknesses in the program or protocol before full scale evaluation.

Sample Size Calculation

The randomized trial is designed as a non-inferiority study to compare the changes in MSEL between 2 interventions. We expect that the change in MSEL score for the subjects in the new intervention arm will be slightly better than that in the control arm by 1.5 units. Assuming the SD of changes in MSEL score is 15 units, with 5 units as the non-inferiority margin, based on a one-sided test with 80% power and 5% significance level, it is sufficient to recruit 132 subjects (66 in each arm). We decided to recruit 200 subjects in total (100 in each arm) after considering withdrawals and lost to follow up. The computation was performed using a proprietary software programmed in R.

Randomisation Process and Blinding

Computer-generated randomisation will be used to randomly assign the participants to one of the intervention groups. Block randomisation will be used to allocate the recruited subjects into one of the interventions. A randomisation list will be generated by the study statistician and envelopes will be prepared. Although the allocation of intervention will be concealed and the study team will not know in advance which subject will receive which intervention, the blinding will not be possible once the intervention is assigned. Assessors of the initial and final MSEL were not told of the intervention status of the patient to avoid bias in outcome assessment. Blinding of the parents is not possible in the context of this study. Phone calls will be made if necessary to confirm appointments and/or before commencing consultation over video conference in the Telerehab group. Parents in both study arms will be encouraged to spend 2h per week in quality interactions with their children.

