Children who meet the inclusionary criteria will be randomly assigned to the standard or telerehab group of the study. Parents will be informed of the randomisation assignment and clinical diagnostic impression on ADOS. Baseline evaluation measures – Mullen's Scales of Early Learning (MSEL), Vineland Adaptive Behaviour Scales (VABS-III), Parenting Stress

Index (PSI-SF), Joint Engagement Rating Inventory (JERI) and FEIQoL (Families in Early Intervention Quality of Life) - will be completed for all.

Data Collection Time Points

The child and parents' skills will be recorded at 4 data points (baseline; 2 midterm reviews; final review) and progress tracked on the IIP, JERI and FSC. Parent questionnaires will be given at the end of the intervention to evaluate parents' experience with the technology used in the sessions, using a Likert Scale, and to evaluate their experience as *providers* of intervention services to their child. Video analyses will be performed by external raters. Inter-rater reliability will be calculated based on the assessments of raters (number of agreements/number of agreements plus disagreements). Hospital resource use pertaining to the intervention will be recorded at each point as well as healthcare expenditures and household resource use, travel expenses and caregiver time spent.

All clinical data will be collected in the case record form designed for the collection of data for the study. For the various assessment tools that will be used, data will be collected on the assessment tool itself, which will serve as the source of that data.

All data will be later transcribed to excel sheets or other relevant databases as soft data for statistical analysis. The data will be coded to remove any patient identifiers before sharing with the statistician for analysis.

Exit Review for Early Withdrawals

If the participant has completed their first block of intervention and requests to withdraw from the study before their final reviews and assessments (Visit 12 to 14), they will be presented with the option to come back to the clinic for an exit review before withdrawing. In the exit review, the child will be assessed on MSEL, parental stress index, parent satisfaction survey, cost survey, FEIQoL and VABS. Specific to the children in the telerehab arm, an additional video recording of parent-child interaction will be done through VC. However, participants can opt to not come back for the exit review and withdraw from the study immediately.

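### Outcome assessment after stopping therapy depends on when and why the child stops, and the plan does not say whether an early exit MSEL counts as the programme-conclusion value

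*Combined protocol and SAP*

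**What the plan says.** Under Exit Review for Early Withdrawals, the offer applies "If the participant has completed their first block of intervention and requests to withdraw from the study before their final reviews and assessments". The review comprises MSEL, the parenting stress index, VABS, FEIQoL and the satisfaction and cost surveys. It takes place before the family withdraws, and the family may decline it.

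Under Transfer to Early Intervention Programs, study therapy continues for 10 weeks after EIPIC enrolment, and "study participants who have been transferred to an EIPIC will still be assessed per protocol for Midterm Progress Reviews and Final Reviews and Assessments". That sentence names EIPIC only. It does not mention children moved to a private service or families who simply stop attending.

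The indicator table defines the MSEL outcome as change from baseline to programme conclusion. Annex 1 lists MSEL at Visits 2-3 and 12-14 only, so no midterm value can serve as a fallback.

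The analysis plan is per-protocol. Children who complete less than 80% of their arm's sessions are excluded, and the control-arm example is 8 of 10 clinic sessions.

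**The concern.** Stopping sessions and leaving the study are different events, but the plan separates them only for EIPIC transfers. This leaves three positions:

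- A child who withdraws before finishing block 1 has no follow-up MSEL provided for. This follows from silence; no other section fills the gap.
- A child who withdraws later may have an MSEL taken when they leave.
- A child transferred to an EIPIC has an MSEL at the scheduled end.

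The second and third values are not the same endpoint, and which one a child has depends on the reason for stopping. The plan does not say whether an exit MSEL counts as the final value, how differences in timing are handled, or how a missing MSEL is handled. In a non-inferiority trial the harmful case is an early value that understates the control arm's gain, because it makes telerehab look closer to control than it is.

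**Working it through.** **The plan's own sample size.** The inputs in Sample Size Calculation are: "with 5 units as the non-inferiority margin, based on a one-sided test with 80% power and 5% significance level"; "Assuming the SD of changes in MSEL score is 15 units"; and a telerehab change "slightly better than that in the control arm by 1.5 units".

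n per arm = 2 × [15 × (1.645 + 0.842) / (5 + 1.5)]² = 65.85, rounded up to 66, or 132 in total. This reproduces the stated figure. Recruiting 200 leaves room for 200 − 132 = 68 children (34%). That is only the loss implied by the two totals. No rate is stated, and it includes loss to follow-up that no exit review would reach.

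**Can an early exit MSEL enter the per-protocol analysis?** Sessions accumulated by the end of each block, from Annex 1:

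| | Block 1 | Block 2 | Block 3 | Block 4 |
|---|---|---|---|---|
| Control | 6 | 10 | 16 | home-based only |
| Telerehab | 6 | 10 | 12 | 18 |

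Thresholds under the 80% rule:

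- Control, by the worked example: 8 of 10, passed during block 2.
- Control, by 16 sessions: 0.8 × 16 = 12.8, so 13, passed during block 3.
- Telerehab, by 18 sessions: 0.8 × 18 = 14.4, so 15, passed only during block 4.

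On the worked example, a control child who leaves after block 2 and accepts an exit review qualifies with an MSEL taken before block 3. A telerehab child leaving at the same point has 10 of 18 sessions and is excluded. Early values could therefore enter mainly in the control arm. If the control threshold is 13 of 16, the gap narrows to block 3 against block 4. The 8-of-10 example conflicts with the 16 control sessions given in the intervention description, Table 1 and both annexes.

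**Illustration only; these inputs are assumed and are not in the documents.** Let a share f of analysed control children have an exit MSEL that is s points below their end value, with no such values in telerehab. The arm difference then shifts by f × s towards telerehab. With 66 per arm, SE = 15 × √(2/66) = 2.61. At a true difference of −5, the chance of wrongly declaring non-inferiority under the planned 95% CI rule is Φ(f × s / 2.61 − 1.96), which is 2.5% with no shift.

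| f | s | Shift | Chance |
|---|---|---|---|
| 5% | 2 | 0.10 | 2.7% |
| 5% | 5 | 0.25 | 3.1% |
| 10% | 2 | 0.20 | 3.0% |
| 10% | 5 | 0.50 | 3.8% |
| 20% | 2 | 0.40 | 3.5% |
| 20% | 5 | 1.00 | 5.7% |

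**The case against.** The exit review is for families leaving the study, whereas EIPIC transfers stay in it, so different schedules are partly to be expected. The optional review already recovers some data. Many early leavers fail the 80% rule whatever MSEL they have. Some families who stop will also refuse a later assessment. All of this stands, and it limits what the change can recover. It does not supply a schedule for children who stop sessions but would return for assessment, nor a rule for using exit values.

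Three stronger readings are tempting, and the documents do not support them.

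- **One-sided loss of JERI.** The exit section says "Specific to the children in the telerehab arm, an additional video recording of parent-child interaction will be done through VC", which might suggest that interaction data are lost in the control arm alone. But JERI is absent from the exit list for both arms. Annex 1 ties the telerehab-only video observation to FSC and NDBI-Fi, and NDBI-Fi is planned in that arm only. The recordings as a whole do also serve JERI, and the word used for the exit recording may imply a clinic recording as well, but neither establishes a difference between arms.
- **A bar on final review.** Program Timeline lets a child move on "only when they have completed all planned sessions in the previous phase". That sentence is framed as a general rule for scheduling delays and is illustrated by baseline preceding intervention. Make-up sessions and missed appointments are allowed for elsewhere. It deserves clarification but is not a proven block.
- **A large bias from block 1 leavers.** A child with 6 sessions fails the 80% rule on 10, 16 or 18 sessions, so that child's early MSEL cannot enter the stated analysis. Selection among completers through unequal loss is a separate matter, and it would remain while the analysis is per-protocol only.

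**Conclusion.** The point holds as a gap in design and definition. Children who leave before the end of block 1 have no post-baseline MSEL provided for. Children who stop sessions for reasons other than EIPIC transfer have no end-of-programme schedule. The status of an exit MSEL is undefined. Under the 8-of-10 example, early values can enter the primary analysis mainly from control children.

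The direction is conditional. It favours non-inferiority only if an early MSEL understates the control child's end value, which the documents do not establish, since MSEL is reported on standardised scales. The size is unknown. The 0.1 to 1.0 point range (2% to 20% of the margin) rests wholly on the assumed shares and shortfalls. The improvement is worth making because it is cheap and because outcomes that were never collected cannot be recovered in analysis.

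**What to change.** 1. Separate stopping sessions from withdrawing from follow-up. Offer every randomised child who stops sessions, in any block and for any reason, the existing Visit 12-14 MSEL, PSI, VABS and FEIQoL at the scheduled end of programme. Define that date for a child who has stopped, because Annex 2 gives only an approximate duration of 40 to 60 weeks.
2. Keep the exit review for families who decline this, and remove its block 1 condition.
3. Record the date of every exit MSEL. State that it is not used as the programme-conclusion value in the primary analysis without allowing for timing.
4. Reconcile the 8-of-10 example with the 16 control sessions.
5. Optionally, add the clinic parent-child recording for JERI to the exit review in both arms, since JERI is compared between arms and the exit list omits it for both.

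The cost is protocol and consent wording, plus up to about 120 minutes (MSEL and PSI) and 60 minutes (VABS) for each family that stopped and accepts. FEIQoL can already be completed by email or telephone. Not all families will accept. The visits exist, and children remain patients of the unit until age 7. Table 4 shows data collection continuing in Year 5 after enrolment closes, so children still in follow-up could benefit. For those who have already left, only the dating and the rule for use can help.

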The profile of the child in terms of their developmental status based on initial evaluation results and an individualised intervention plan (IIP) will be discussed by the therapist with parents. The therapist will coach parents in the context of clinic-based play activities and help parents identify contexts and activities at home where the parents could follow up on the program at home. Children and their parents will receive the standard program which consists of 16 clinic-based intervention sessions of 60 min each, separated into 3 intervention blocks, with breaks in between so that parents will have opportunities to practise at home. This arrangement also allows parents who had missed their scheduled sessions to have make-up sessions during the breaks. Intervention sessions empower and equip parents with skills and strategies to engage with their child at home. Since the program involves behavioural intervention and parent coaching, active participation of parent and child are key to each session. However, realistic challenges in terms of child/parent or therapist being unwell, or when the

parent has work related commitments, may require rescheduling or cancellation of some visits. These are not anticipated to have any adverse impact on the child's health or the study.

Intervention: Telerehab Program

The intervention will commence with 2 clinic-based intervention sessions of 60 min each to provide adequate opportunity to engage in relational family-centred practices, joint decision and planning of the IIP based on initial evaluations and explore effective strategies as foundation to the subsequent interactions and coaching through VC.

Setting: Prior to intervention sessions, the therapist and parent will discuss and identify a suitable and feasible location to place the devices of their choice that would provide clear unobstructed views of parent-child interactions and activities. For 16 sessions, the therapist and parent will log onto the MOHH VC portal for the VC call.

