Protocol deviation is defined as any divergence from what was pre-planned and approved by the institutional review board. As the study is conducted as part of routine care and operations, there are practical constraints that may cause protocol deviations to occur. Rescheduling of appointments by the parents (e.g. due to work constraints, child's sickness, other events) or defaulting appointments is inevitable. Hence, for per-protocol analyses, we will only exclude participants with major protocol deviation, which will be defined as participants who do not complete 80% of the intended therapy sessions allocated for their study arm. This means that a control arm participant must attend at least 8 out of 10 clinic-based sessions. For the remaining 2 sessions, participants can either be attending it through video-conferencing (due to the COVID-19 pandemic) or miss the appointment.

Quantitative Outcomes

For the randomized trial, since the study is a non-inferiority study, statistical analysis will be carried out on a per-protocol basis. Subjects with any major protocol deviation as defined above will be excluded from the final analysis.

All demographic, clinical and cost characteristics will be analysed descriptively. Mean (SD) or median (range), whichever is more appropriate will be reported for numerical variables, while N (%) will be reported for categorical variables. 2-sample t-tests, or Mann-Whitney U tests will be used to compare the change of MSEL score between 2 arms. Mean difference and 95% CI will be estimated. If the lower boundary of the 95% CI is more than -5, non-inferiority will be declared. Changes in the quality of parent-child engagement, parental stress index score, and adaptive score will be compared by using either a 2-sample t-test, or a Mann-Whitney U test, whichever is more appropriate. Linear regression will be used to adjust for any covariates.

Cost-Effectiveness Analysis

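### The per-protocol rule sets the control threshold at 8 of 10 sessions, but the control course is 16 sessions, so 80% means 13 and the same child can be classified two ways

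*Combined protocol and SAP*

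**What the plan says.** The section headed Protocol Deviation and Per-protocol Analysis restricts exclusion to major deviators, defined as "participants who do not complete 80% of the intended therapy sessions allocated for their study arm". The next sentence turns this into a number for one arm: "This means that a control arm participant must attend at least 8 out of 10 clinic-based sessions". The sentence after that disposes of the balance: "For the remaining 2 sessions, participants can either be attending it through video-conferencing (due to the COVID-19 pandemic) or miss the appointment". No number is written for telerehab.

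Under Quantitative Outcomes, the analysis is per-protocol because the trial is a non-inferiority study, and "Subjects with any major protocol deviation as defined above will be excluded from the final analysis". No other analysis set is named for the non-inferiority test.

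The section Intervention: Standard Program describes a "standard program which consists of 16 clinic-based intervention sessions of 60 min each, separated into 3 intervention blocks". Table 1 of the cost-effectiveness section, Annex 1 and Annex 2 also give 16 control sessions.

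**The concern.** The definition and its worked example cannot both hold for a 16-session course. The example cannot be taken as shorthand for a ratio, because the following sentence allocates the two sessions left over, which makes 10 a count. No section describes a 10-session control course or explains where the 10 comes from.

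This rule decides who enters the primary comparison. Two analysts following the text in good faith could build different control groups. If the choice were made once outcomes were known, in a trial where parents and therapists know the allocation, it would be an unplanned decision about the primary dataset. If the count replaced the percentage for control only, the arms would be held to different standards: as little as half the course for control, against 80% for telerehab.

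Short attendance is foreseeable. The plan itself says that "defaulting appointments is inevitable".

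**Working it through.** **Inputs**

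| Item | Value | Where |
|---|---|---|
| Completion required | 80% of the sessions allocated to the arm | Protocol Deviation and Per-protocol Analysis |
| Worked control minimum | 8 of 10, with 2 remaining | same section |
| Control course | 16 | Intervention: Standard Program; Annex 2 |
| Control course, from therapy time | 720/45 = 16 and 240/15 = 16 | Table 1 |
| Control course, by block | 6 + 4 + 6 = 16 | Annex 1 |
| Telerehab course | 2 clinic + (4 + 4 + 2 + 6 = 16) video = 18 | Annex 1; Annex 2 |

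**The plan's own figure.** 0.80 × 10 = 8, and 10 − 8 = 2 remaining. This works only with a denominator of 10. The one way to reach 10 from the schedule is blocks 1 and 2 alone (6 + 4), and the rule is not limited to those blocks.

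**The definition applied to the documented courses.** Threshold = 0.80 × allocated sessions, rounded up.

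- Control: 0.80 × 16 = 12.8, so 13 (13/16 = 81.25%), leaving 16 − 13 = 3.
- Telerehab: 0.80 × 18 = 14.4, so 15 (15/18 = 83.3%), leaving 18 − 15 = 3.

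**Where the two sentences disagree for a control child**

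*Reading (a): any 8 sessions.* Totals of at least 8 and below 13 are in conflict: 8, 9, 10, 11 and 12, or 50% to 75% of the course. All are kept by the count and excluded by the 80% definition. Totals of 7 or fewer, or 13 or more, are classified the same way by both.

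*Reading (b): 8 of the 10 sessions in blocks 1 and 2.* Take 0–10 sessions attended in blocks 1 and 2 and 0–6 in block 3, which gives 11 × 7 = 77 possible patterns.

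- Kept by the count, excluded by 80%: 8 with 0–4, 9 with 0–3, 10 with 0–2, so 5 + 4 + 3 = 12 patterns. For example, 8 + 4 = 12.
- Excluded by the count, kept by 80%: one pattern, 7 + 6 = 13.
- Totals of 8 to 12 that fail both: 20 patterns. For example, 7 + 5 = 12.

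These are possible patterns, not expected numbers of children.

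**Illustration of size, reading (a) only.** The documents give no attendance rate. Assume independent attendance at each of 16 sessions with probability p, so that the number attended is binomial:

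| p (assumed) | P(at least 8) | P(at least 13) | Classified differently |
|---|---|---|---|
| 0.90 | 1.000 | 0.932 | 7% |
| 0.80 | 0.999 | 0.598 | 40% |
| 0.75 | 0.993 | 0.405 | 59% |

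Real attendance is unlikely to be independent from session to session, so this shows only that the answer is sensitive to attendance.

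**Video sessions in the control arm.** The worked sentence counts clinic-based sessions only; the definition does not mention mode. A control with 12 clinic sessions and 1 by video reaches 13 only if video counts.

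**The case against.** The strongest reply is that the section has one operative definition, the 80% rule, and that the exclusion sentence points back to it. The count is introduced as a consequence of that rule, so it can be treated as an example with a wrong denominator. The thresholds are then determinable and nearly even between arms (13/16 and 15/18). This is a fair reading, and unequal standards do arise only if the count is actually used for control. But the count is the only number written down, and the sentence on the remaining two sessions builds on it. The text does not say which of the two governs.

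A second reply is that few children may fall in the disputed range. Missed sessions can be recovered: "This arrangement also allows parents who had missed their scheduled sessions to have make-up sessions during the breaks". Under Program Timeline, a child moves to the next phase "only when they have completed all planned sessions in the previous phase". Both should make short courses less common. They do not rule them out: the plan offers an exit MSEL to families who withdraw after the first block, and final assessments to children who have transferred to other services. Whether exit-review scores enter the comparison is not stated, so the practical effect is uncertain in both directions.

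Third, reading (b) has no support in the text. That is accepted. It is shown because it is the only arithmetic source of the 10, and it does not remove the conflict.

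**Conclusion.** The point holds. The worked control threshold does not follow from the plan's own definition and course length: it should be 13 of 16, not 8 of 10, if the 80% rule and the 16-session course stand. Under the plainest reading, five attendance totals (8 to 12) are classified in opposite ways, down to 50% of the course.

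Because this rule fixes the only population named for the non-inferiority test, it has to be settled before that population is formed. The effect on the MSEL difference cannot be stated in size or direction; both depend on which reading is used, on actual attendance and on whether attendance drives benefit. The conclusion rests on the documents' session counts alone and not on the illustrative attendance rates.

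**What to change.** Before the final analysis, and without looking at MSEL results by arm:

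1. Reconcile the 10 in the per-protocol section with the 16 in Intervention: Standard Program, Table 1, Annex 1 and Annex 2.
2. Apply the stated 80% to the agreed course length in both arms and write both thresholds: at least 13 of 16 and at least 15 of 18 if those lengths stand.
3. Bring the allowance for the remaining two sessions into line with that denominator (16 − 13 leaves 3).
4. State whether control sessions held by video count towards the minimum.
5. Report how many controls are classified differently by the worked count and by the corrected rule, and which reading of the count was used.

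The cost is a few sentences. Table 2 already plans to capture therapy sessions attended; a comparison under reading (b) would also need attendance by block.

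The per-protocol set may be smaller than under the 8-session count, by an amount that cannot be predicted. The plan recruits 100 per arm against a stated need of 66, a difference of 34 that must also cover withdrawals. That 66 assumes a one-sided 5% test, whereas the decision rule uses the lower limit of a 95% CI. On the plan's other inputs (SD 15, margin 5, expected advantage 1.5, 80% power), that limit needs 2 × 15² × (1.96 + 0.8416)² / 6.5² = 83.6, so 84 per arm, leaving 100 − 84 = 16. The room for exclusions is therefore tighter than it appears.
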